5.3.1 Demographics and baseline characteristics

The following demographics and baseline characteristics will be summarized for the safety and ITT populations:

- Weight (kg)
- Height (cm)
- Body mass index (BMI) in kg/m² as quantitative variable documented in the eCRF and in categories (<30 kg/m², ≥30 kg/m²)
- Age in years as quantitative variable and in categories (<65 years, ≥65 years)
- Sex (Male, Female)
- Race (White, Black or African American, Not Reported, Unknown, Other, Multiple)
- Ethnicity (Hispanic or Latino, not Hispanic or Latino, Not Reported, Unknown, Other Ethnicity)
- Country (Czech Republic, Hungary, Serbia, Poland, United States)

Baseline safety and efficacy parameters (apart from those listed above) will be presented with the relevant safety and efficacy summaries.

5.3.2 Medical (or surgical) history

Medical (or surgical) history includes all relevant medical (or surgical) history during the lifetime of the participant. Medical and surgical history will be coded to a LLT, PT, HLT, HLGT, and associated primary SOC using the MedDRA version currently in effect at Sanofi at the time of database lock.

Medical and surgical history will be summarized by SOC and PT for the ITT population, sorted by internationally agreed order of SOC and by the decreasing frequency of PT within SOC.

5.3.3 Disease characteristics at baseline

Specific disease characteristics at baseline includes the following variables and variables related to diabetes history will be summarized for the Safety and ITT populations:

- Baseline HbA1c as quantitative variable and in categories (<8.5%, ≥8.5%)

- Baseline FPG
- Baseline SMPG
- eGFR as quantitative variable and in categories (<45 mL/min/1.73 m²; ≥45 mL/min/1.73 m²)
- Previous use of anti-hyperglycemic therapy by medication categories (SU, Metformin, GLP-1Ras, DPPIV Inhibitors/Gliptins, SGLT2 inhibitors, TZD/Glitazones, Insulin, Other)
- Anti-hyperglycemic therapy currently taken (Yes, No)
- Age (years) at diagnosis of diabetes
- Duration of diabetes (time from diagnosis (years))
- History of gestational diabetes (Yes, No)

Continuous variables will be summarized using descriptive statistics. Categorical disease characteristic variables will be summarized using count and percentages.

5.3.4 Prior and concomitant medications

All medications will be coded using the World Health Organization-Drug Dictionary (WHO-DD) using the version currently in effect at Sanofi at the time of database lock.

- Prior medications are those the participant used prior to first investigational medicinal product (IMP) intake. Prior medications can be discontinued before first IMP administration or can be ongoing during the treatment and/or post-treatment period.
- Concomitant medications are any interventions received by the participant concomitantly to the IMP during the on-treatment period. A medication may be classified both as a prior and concomitant medication. Concomitant medications do not include medications started during the post-treatment period (as defined in [Section 4.1](#))
- Post-treatment medications are those the participant continued or started during the post-treatment period (as defined in [Section 4.1](#)).
- Any technical details related to computation, dates, or imputation for missing dates are described in [Section 5.4.4](#)).

Prior, concomitant, and post-treatment medications will be summarized by anatomic and therapeutic levels defined by ATC (Anatomic Therapeutic Chemical) classification for the ITT population and will be presented by treatment arm and overall.

Prior medication summaries will be sorted by decreasing frequency of anatomic class (ATC1) and therapeutic class (ATC2) based on overall incidence. In case of equal frequency (anatomic or therapeutic categories), alphabetical order will be used. Participants will be counted once in each ATC category (anatomic or therapeutic) linked to the medication. A medication may be counted in several anatomic categories.

Concomitant and post-treatment medication summaries will be sorted by decreasing frequency of anatomic class (ATC1) followed by therapeutic class (ATC2) based on incidence in the Gla-300 arm. In case of equal frequency regarding ATCs, alphabetical order will be used. Participants will be counted once in each ATC (anatomic or therapeutic categories) linked to the medication. A medication may be counted in several anatomic categories.

5.3.4.1 Non-antidiabetic medications

Prior, concomitant, and post-treatment non-antidiabetic medications will be summarized by anatomic class (ATC1) and therapeutic class (ATC2) for the ITT population and will be presented by treatment arm and overall.

Prior medication summaries will be sorted by decreasing frequency of anatomic class (ATC1) and therapeutic class (ATC2) based on overall incidence. In case of equal frequency (anatomic or therapeutic categories), alphabetical order will be used. Participants will be counted once in each ATC category (anatomic or therapeutic) linked to the medication. A medication may be counted in several anatomic categories.

Concomitant and post-treatment medication summaries will be sorted by decreasing frequency of anatomic class (ATC1) followed by therapeutic class (ATC2) based on incidence in the Gla-300 arm. In case of equal frequency regarding ATCs, alphabetical order will be used. Participants will be counted once in each ATC (anatomic or therapeutic categories) linked to the medication. A medication may be counted in several anatomic categories.

An individual listing sorted by treatment arm and subject number will be populated instead of a summary table if few non-antidiabetic medications are observed either prior or post treatment.

5.3.4.2 Antidiabetic medications

Prior, concomitant, and post-treatment antidiabetic medications will be summarized by pharmacological class (ATC3), chemical class (ATC4) and standardized medication name for the ITT population and will be presented by treatment arm and overall.

The table for antidiabetic prior medications will be sorted by decreasing frequency of pharmacological class followed by chemical class and standardized medication name based on the overall incidence across treatment arm. In case of equal frequency, alphabetical order will be used.

The tables for antidiabetic concomitant and post treatment medications will be sorted by decreasing frequency of pharmacological class followed by chemical class and standardized medication name based on the incidence in the Gla-300 treatment arm. In case of equal frequency, alphabetical order will be used.

In addition, the following specific medications will be summarized:

- Antidiabetic concomitant rescue medications will be presented by pharmacological class (ATC3), chemical class (ATC4) and standardized medication name. [Table 9](#) below defines antidiabetic medications by pharmacological class (ATC3).

- Prohibited concomitant medications will be presented by prohibited medication category (as defined by deviation) and standardized medication name (see [Table 8](#) below).

Table 8 - Prohibited Medications

Prohibited Medication Category	Pharmacological Class (ATC3)	Standardized Medication Name (ATC4) ^a
Insulins and analogues	A10AB, A10AC, A10AD, A10AE, A10AF	
Other blood glucose lowering drugs, excluding insulins	A10BX	Tirzepatide (ATC5: A10BX16)
Peripherally acting antiobesity products	A08AB	
Thyroid hormones	H03AA	
Corticosteroids (excluding inhaled and topical)	H02A, H02B	
Salicylic acid and derivatives	N02BA	
Ascorbic acid (Vitamin C), including combinations	A11GA, A11GB, G01AD, S01XA	Ascorbic acid (G01AD03), Ascorbic acid (S01XA15)

^a Standardized medication names are provided where the prohibited medication is limited to certain medications within the provided ATC3 class.

A list of ATC3 codes to be used in identifying antidiabetic medications is shown in [Table 9](#) below. Prior, concomitant and post-treatment antidiabetic non-insulin and rescue therapies will also be summarized per standardized drug grouping name and standardized medication name.

Table 9 - Antidiabetic Medications

Standardized Drug Grouping Name	Group ID	Pharmacological Class (ATC3)
Insulins and analogues	100	A10AB, A10AC, A10AD, A10AE, A10AF
Biguanides	101	A10BA
Sulphonamides	102	A10BC
Other blood glucose lowering drugs	103	A10BX
Other drugs used in diabetes	104	A10X
Alpha glucosidase inhibitors	105	A10BF
Thiazolidinediones	106	A10BG
Dipeptidyl peptidase-4 inhibitors	107	A10BH
Glucagon-like peptide-1 (GLP1) agonists	168	A10BJ
SGLT2 inhibitors	291	A10BK

5.4 APPENDIX 4 DATA HANDLING CONVENTIONS

5.4.1 Demographic formulas

Age (years) = (Year of informed consent date - Year of birth)

5.4.2 Disease characteristics formulas

Duration of diabetes (years)= (Date of informed consent - Date of diagnosis of diabetes
+ 1)/365.25

Age at diagnosis of diabetes (years) = Year of diagnosis of diabetes - Year of birth

5.4.3 Reference date, study day, and baseline

For efficacy analyses, the reference date is a participant's randomization date. For safety assessments, the reference date is a participant's first treatment date.

Study day is calculated as (Date of assessment - Reference date) + 1.

Baseline is the last non-missing value recorded prior to or on the reference date.

5.4.4 Missing data

For relevant categorical tabulations in demographics, baseline characteristics and compliance summaries, the number of participants with missing data are counted in a category of "Missing" but no percentages will be calculated. "Missing" category will only be presented in summaries for variables where missing data occurs. The percentages on the other rows will be based on the number of non-missing observations.

Medication missing/partial dates

No imputation of medication start/end dates or times will be performed. If a medication date or time is missing or partially missing and it cannot be determined whether it was taken prior, concomitantly, or post-treatment, it will be considered as a prior, concomitant, and post-treatment medication.

Adverse events and Hypoglycemic events with missing or partial date/time of onset

Missing or partial adverse event onset dates and times will be imputed so that if the partial adverse event onset date/time information does not indicate that the adverse event started prior to treatment, the adverse event will be classified as treatment emergent. These data imputations are for categorization purpose only and will not be used in listings. No imputation is planned for date/time of adverse event resolution.

Missing date and time of first IMP administration

When the date and time of the first IMP administration is missing, all adverse events that occurred on or after first dose day defined by the eCRF should be considered as treatment-emergent adverse events.

The exposure duration will be kept as missing.

Missing severity of adverse events

If the severity is missing for 1 of the treatment-emergent occurrences of an adverse event within data collection per MedDRA PT, the maximal severity on the remaining occurrences will be considered. If the severity is missing for all the occurrences, a “missing” category will be added in the summary table.

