4.7 SAFETY ANALYSES

All safety analyses will be performed on the safety population as defined in [Section 3](#), unless otherwise specified, using the common rules:

- The analysis of the safety variables will be essentially descriptive, and no formal hypothesis testing is planned.
- Safety data in participants who do not belong to the safety population (eg, exposed but not randomized) will be provided separately.

The observation period of safety data will be divided into 3 periods as defined below:

- **Pre-treatment period:** the time between the date of signed informed consent and the first injection of the open-label study drug.
- **On-treatment period:** the time from the first injection of the open-label study drug up to 7 days after the last injection of the open-label study drug, regardless of the introduction of rescue therapy. The 7-day interval is chosen based on the half-life of the study drug (approximately 5 times the half-life of IDeg-100).
- **Post-treatment period:** the time starting 8 days after the last injection of the open-label study drug.

The denominator for computation of percentages is the safety set within each treatment arm unless otherwise specified.

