4.7.3 Adverse events

General common rules for adverse events (AEs)

All AEs will be coded to a lower-level term (LLT), preferred term (PT), high-level term (HLT), high-level group term (HLGT), and associated primary system organ class (SOC) using the Medical Dictionary for Regulatory Activities (MedDRA) currently in use by the sponsor at the time of database lock.

The AEs will be analyzed in the following 3 categories (as defined by study periods for the safety analyses):

- Pre-treatment AEs: AEs that developed, worsened or became serious during the pre-treatment period.
- Treatment-emergent adverse events (TEAEs): AEs that developed, worsened or became serious during the on-treatment period
- Post-treatment AEs: AEs that developed or worsened, or became serious during the post-treatment period

Similarly, deaths will be analyzed in the pre-treatment, treatment-emergent and post-treatment periods.

The primary focus of AE reporting will be on TEAEs. Pre-treatment and post-treatment AEs will be described separately.

An AE with incomplete or missing date/time of onset (occurrence, worsening, or becoming serious) will be classified as a TEAE unless there is definitive information to determine it is a pre-treatment or a post-treatment AE.

If the assessment of the relationship to IMP is missing for an AE, this AE will be assumed as related to IMP. If the severity is missing for 1 of the treatment-emergent occurrences of an AE, the severity will be imputed with the maximal severity of the other occurrences. If the severity is missing for all the occurrences, the severity will be left as missing.

Multiple occurrences of the same event in the same participant will be counted only once in the tables within a treatment phase.

The AE tables will be sorted as indicated in [Table 5](#).

Table 5 - Sorting of AE tables

AE presentation	Sorting rules
SOC, HLGt, HLT and PT	By the internationally agreed SOC order and by alphabetic order of HLGts, HLTs and PTs.
SOC and PT	By the internationally agreed SOC order and decreasing frequency of Pts ^{a,b}

a Sorting will be based on the Gla-300 group/overall incidence. In case of equal frequencies of PTs within a SOC, the alphabetic order will be applied.
b The table of all TEAEs presented by SOC and PT will define the presentation order for all other tables (eg, treatment-emergent SAE) presented by SOC and PT, unless otherwise specified.

Analysis of all adverse events

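### SAP 5.4.4 and SAP 4.7.3 give conflicting rules for adverse events with a missing or partial onset, and the SAP does not say which one prevails

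*SAP*

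**What the plan says.** Section 4.7 of the SAP splits safety observation into three periods. The on-treatment period is "the time from the first injection of the open-label study drug up to 7 days after the last injection of the open-label study drug". The post-treatment period is "the time starting 8 days after the last injection of the open-label study drug". Section 4.7.3 defines TEAEs as "AEs that developed, worsened or became serious during the on-treatment period" and provides for pre-treatment and post-treatment AEs to be described apart from them.

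For incomplete onsets there are two rules.

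- SAP 4.7.3, under the common rules for AEs: an event with an incomplete or missing onset "will be classified as a TEAE unless there is definitive information to determine it is a pre-treatment or a post-treatment AE". This gives two exceptions.
- SAP 5.4.4, in the paragraph headed "Adverse events and Hypoglycemic events with missing or partial date/time of onset", sets the category by imputation: if what was recorded of the onset "does not indicate that the adverse event started prior to treatment, the adverse event will be classified as treatment emergent". This gives one exception, for a pre-treatment start.

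Section 5.4.4 adds: "These data imputations are for categorization purpose only and will not be used in listings". Protocol 8.8 leaves missing AE dates to the SAP, so it does not settle the difference.

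**The concern.** An AE recorded with only a month, where the whole month falls after the on-treatment period, is a post-treatment event under 4.7.3 and a TEAE under 5.4.4. Section 5.4.4 also covers missing times. Read literally, an event with a full calendar date weeks after the last injection but no clock time would be treatment-emergent.

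Two programmers working from this SAP could therefore produce different TEAE tables from the same data. One of those versions would attribute to the randomized insulin events that the SAP's own definitions place after the treatment period. The abbreviated CSR keeps TEAE Tables 14.3.1 to 14.3.5 (SAP 5.6), so the point still bears on what will be reported after the early termination.

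**Working it through.** The plan gives no figure to reproduce here. The check is to apply both rules to the same onsets and see where they part.

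**Inputs.** The two rules (SAP 4.7.3 and 5.4.4) and the period limits (SAP 4.7): on treatment from first injection to last injection + 7 days, post-treatment from last injection + 8 days. The illustrative patient is an assumption: first injection 10 Jan 2023, last injection 10 Mar 2023. The on-treatment period then ends on 17 Mar and the post-treatment period starts on 18 Mar 2023. A month or year counts as definitive only if it lies wholly in one period.

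| Recorded onset | SAP 4.7.3 | SAP 5.4.4 |
|---|---|---|
| Fully missing | TEAE | TEAE |
| Dec 2022 | Pre-treatment | Pre-treatment |
| Jan 2023 | TEAE | TEAE |
| Feb 2023 | TEAE | TEAE |
| Mar 2023 | TEAE | TEAE |
| Year 2023 only | TEAE | TEAE |
| Apr 2023 | Post-treatment | TEAE |
| May 2023 | Post-treatment | TEAE |
| 20 May 2023, time missing | Post-treatment | TEAE |

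The rules agree for fully missing, ambiguous and pre-treatment onsets. They disagree only where the information puts onset at last injection + 8 days or later. With the 4.7.3 exception added to 5.4.4, the last three rows become post-treatment and no other row changes.

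**Direction.** The events called TEAE under 5.4.4 are those called TEAE under 4.7.3 plus the disputed class. This takes both sections to require the same strength of evidence for a pre-treatment onset. Under 5.4.4 the TEAE count is then equal or higher, never lower.

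**Room for the disputed class.** Take a last injection on Day d and follow-up to the Week 25 contact on Day 175. Post-treatment days = 175 − (d + 8) + 1 = 168 − d.

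- d = 28: 140 days
- d = 84: 84 days
- d = 140: 28 days
- d = 168 (completer): 0 days, or 178 − 176 + 1 = 3 days if the contact is at the late end of its ±3-day window

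For serious AEs, Protocol 6.2.6.4 sets reporting to 30 days after the last dose, so Days 8 to 30 after that dose give 30 − 8 + 1 = 23 post-treatment days even for a completer.

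These are days in which such an event could occur, not events. The documents give no AE data and no frequency of partial dates, so no event count follows from them.

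**The case against.** The best defense is that 4.7.3 already states the right rule, under general rules for AEs, and that 5.4.4 is an appendix of data conventions that is merely silent on post-treatment onset. Read together, 4.7.3 supplies the missing exception and no event moves. That reading is reasonable, but nothing in the SAP requires it. Section 5.4.4 is worded as a complete rule, and its stated purpose is to set the category. The medication rule in the same section applies its default only where timing cannot be determined, a safeguard the AE rule lacks. The ambiguity stands.

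The defense does defeat several stronger readings that a reader might infer.

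- *That TEAE counts are inflated.* This needs 5.4.4 to override 4.7.3, and no text says so.
- *That a large share of events is at risk.* For stops on Days 42, 84 and 112, post-treatment days are 126, 84 and 56 of 175, or 72%, 48% and 32%. These are shares of planned follow-up days, not of events or partial dates. They also assume follow-up to the scheduled end under Protocol 4.4.1.1, whereas Protocol 3.1.2 describes a 7-day follow-up after premature discontinuation. The sponsor stopped the study on 27 June 2023 (SAP 1.1), and the documents do not say how long patients off drug were then followed.
- *That post-treatment AE tables would be understated.* Those tables are in the full plan (SAP Table 6), but the reduced output list in SAP 5.6 contains none. The listing of all AEs (16.2.7.1) would still show the onset as recorded.
- *That on-treatment hypoglycemia is overstated.* Only the 5.4.4 heading names hypoglycemic events; the rule itself speaks of adverse events. Hypoglycemia has its own form recording onset date and time.
- *That one arm is favored.* This would need unequal early discontinuation, on which the documents give no data.

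**Conclusion.** The conflict is real on the face of the text: two rules, opposite answers for one class of event, and no stated precedence. Followed as written, 5.4.4 breaks the SAP's own period definitions and can only push TEAE counts up. Whether any count is affected depends on which rule is programmed and on how many partial onsets fall wholly after last injection plus 7 days. That number is unknown and probably small, because completers have almost no post-treatment window for non-serious AEs. The exposure lies mainly with early discontinuers and with serious AEs in the 30-day reporting window. Safety analyses are descriptive (SAP 4.7), so no hypothesis test depends on this. It is a minor point, worth correcting because it affects whether the retained TEAE tables can be reproduced.

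**What to change.** Amend SAP 5.4.4 to match 4.7.3: an event with a missing or partial onset is treatment-emergent unless the available information shows that it started before the first injection or after the end of the on-treatment period (last injection plus 7 days). A cross-reference from 5.4.4 to the 4.7.3 rule would serve equally well. State in the text, not only in the heading, whether the same rule covers hypoglycemic events.

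The cost is one clause in the SAP and one condition in the program. If programming is already complete, record in the CSR which rule was applied.

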5.4.5 Analysis windows for time points

5.4.5.1 Main Study

The following analysis windows will decide how the scheduled and/or unscheduled visits will be used in the by-visit analyses of efficacy and safety variables, excluding fasting SMPG (Section 4.4.1.1), SMPG 7-point profile (Section 4.4.1.1), and basal insulin dosing data (Section 4.5.1).

All non-missing measurements (scheduled or unscheduled) will be used if the measurement date is within the analysis window.

After applying these time windows, if multiple assessments are associated to the same time point, the assessment closest from the targeted study day will be used. If the difference is a tie between multiple assessments, the value after the targeted study day will be used. If multiple valid values exist within a same day, then the first value of the day will be selected.

If there is no measurement for a given parameter in an analysis window, data will be considered missing for the corresponding visit.

Table 10 - Analysis window definition

Scheduled post-baseline visit	Targeted study day	Analysis window in study days
Week 4 (Visit 6)	29	Day 2 to Day 43
Week 8 (Visit 10)	57	Day 44 to Day 71
Week 12 (Visit 14)	85	Day 72 to 127
Week 24 (Visit 17)	169	≥ Day128

Study days are calculated considering Day 1 as the day of first administration of intervention (or the day of randomization for participant not exposed).

Unscheduled visits

Unscheduled visit measurements of laboratory data and vital signs will be used for computation of baseline, the last on-treatment value, analysis according to PCSAs, and the shift summaries for safety. They will also be included in the by-visit summaries if they are windowed to scheduled post-baseline visits.

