4.4.2 Lost to Follow-Up

Patients will be considered lost to follow-up if they repeatedly fail to return for scheduled visits and are unable to be contacted by the site.

The following actions must be taken if a patient fails to return to the clinic for a required trial visit:

- The site must attempt to contact the patient and reschedule the missed visit as soon as possible. The patient should be counselled on the importance of maintaining the assigned visit schedule and asked whether they wish to and/or should continue in the trial.
- Before a patient is deemed lost to follow-up, the investigator or designee must make every effort to regain contact with the patient. The methods to contact the patient include 2 phone calls or local equivalent methods (eg, sending an email to patient's last known email address). These contact attempts should be documented in the patient's source documents.

If the patient continues to be unreachable, they will be considered to have withdrawn from the trial.

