4.4.3 Handling of Withdrawals

Patients are free to withdraw from the trial at any time upon request. Their participation in the trial may be stopped at any time at the discretion of the investigator or at the request of the sponsor.

If the patient withdraws consent for disclosure of future information, the sponsor may retain and continue to use any data collected before such a withdrawal of consent.

If a patient withdraws from the trial, they may request destruction of any samples taken and not tested, and the investigator must document this in the site trial records.

Patients who permanently discontinue the study drug or active participation in the trial will no longer receive the study drug. When a patient withdraws from the trial, the reason(s) for withdrawal shall be recorded by the investigator on the relevant page of the eCRF.

A patient may withdraw from the trial or study drug treatment for circumstances that include, but are not limited to, the following:

- The patient intends to become pregnant.
- The patient may be withdrawn at the discretion of the investigator due to noncompliance or due to a safety concern.

- The patient will be withdrawn if they are starting any drugs that interfere with glucose metabolism (eg, systemic glucocorticoid therapy).
- If the fasting or the mean SMPG value is >300 mg/dL, the investigator will schedule an unplanned visit as soon as possible, to obtain confirmatory FPG and investigate the cause. If no apparent or intercurrent cause is detected, the patient may be withdrawn.
- The patient has recurrent severe hypoglycemia or recurrent nocturnal hypoglycemia during the treatment period that poses a potential risk to the patient, as judged by the investigator.
- The patient needs dialysis, as judged by the investigator.
- The patient is unable to comply with the trial protocol, at the investigator's discretion.

All patients who discontinue study drug treatment will be followed up per the methods specified in this protocol. All patients who withdraw from the trial prematurely will, as soon as possible, undergo all end-of-trial and follow-up assessments/procedures at a visit that should be identified as "the early trial discontinuation visit." Patients who fail to return for final assessments will be contacted by the site in an attempt to have them comply with the protocol requirements.

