6.1 Efficacy Assessments

6.1.1 HbA1c Measurements

The primary efficacy endpoint and some secondary and exploratory endpoints will be assessed by HbA1c measurement. Blood samples will be collected to measure HbA1c at the different time points specified in the SoE ([Section 13.2](#)) at the central laboratory.

For the eligibility assessment, HbA1c levels will be measured during the screening period (Week –2, Visit 1). For the efficacy assessments of the trial, HbA1c levels will be measured at baseline/randomization, at the end of the titration period (Week 12; Visit 14), and at the end of the treatment period (Week 24, Visit 17; [Section 13.2](#)). If a patient needs to receive rescue antidiabetic therapy, the HbA1c assessment should be performed before they are introduced. In addition, in case of study drug treatment discontinuation, patients will be followed up per protocol. In case of trial discontinuation, HbA1c assessment will be performed at the time of withdrawal, if possible.

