4.3 PRIMARY ENDPOINT ANALYSIS

4.3.1 Definition of endpoint

The primary endpoint is the change from baseline to Week 24 in HbA1c level. For efficacy assessments of the trial, HbA1c will be measured with blood samples collected at the central laboratory at the time points specified in [Section 5.7](#) (baseline, Week 12, Week 24). If a participant needs to receive a rescue antidiabetic therapy, the HbA1c assessment should be performed before the antidiabetic therapy is introduced. In addition, in case of study drug treatment discontinuation, participants will be followed up per protocol. In case of trial discontinuation, HbA1c assessment will be performed at the time of withdrawal. If HbA1c measurements fall out of windowed assessments (baseline, Week 12, Week 24), the results for those assessments will be excluded (considered as missing for analysis).

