Abbreviations: AE, adverse event; AESI, adverse event of special interest; BMI, body mass index; cc1; CKD, chronic kidney disease; CKD-EPI, Chronic Kidney Disease Epidemiology Collaboration; cr, creatinine; DBP, diastolic blood pressure; DTP, direct-to-patient; eDiary, electronic diary; eGFR, estimated glomerular filtration rate; FPG, fasting plasma glucose; Gla-300, insulin glargine 300 U/mL; HbA1c, glycosylated hemoglobin; HCP, healthcare provider; IDeg-100, insulin degludec 100 U/mL; IMP, investigational medicinal product; SAE, serious adverse event; SBP, systolic blood pressure; Scr, serum creatinine; SMPG, self-measured plasma glucose; WOCBP, women of childbearing potential.

- a During the titration period, the doses of Gla-300 and IDeg-100 will be adjusted using a recommended dose-adjustment algorithm. After randomization, the dose will be titrated at least weekly (but no more than every 3 days) until the patient reaches a target fasting SMPG value of 80 to 100 mg/dL (4.4 to 5.6 mmol/L) while avoiding hypoglycemia episodes. Thereafter, until the end of the trial, the doses of Gla-300 and IDeg-100 will be adjusted to maintain this glycemic target, if deemed appropriate by the investigator. Dose adjustments will be based on a median of fasting SMPG values from the last 3 measurements, including the value on the day of titration, measured by the patient using glucose meters and accessories supplied by the sponsor through a vendor. Best efforts should be made to reach the glycemic target by 8-12 weeks after randomization.
- b cc1
- c At the end of the trial, patients should discuss with the investigator, in collaboration with their HCP, whether to continue on the Gla-300 or IDeg-100 treatment regimen or transition to an alternate antihyperglycemic therapy. All patients who withdraw from the trial prematurely will, as soon as possible, undergo all end-of-trial and follow-up assessments/procedures at a visit that should be identified as "the early trial discontinuation visit."
- d An unscheduled visit can be planned anytime during the treatment period if study drug resupply is required. This will be a site visit or via phone contact with DTP-IMP delivery. The sponsor-approved courier company will need at least 72 hours' notice to collect treatment kits from a trial site.
- e This will be a phone contact, but could be a site visit if ongoing or new AEs emerge during the post-treatment period, if necessary.

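### Should HbA1c and FPG drawn at an early trial discontinuation visit on Days 128–165 be kept out of the Week 24 analysis window?

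*SAP*

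**What the plan says.** SAP 5.4.5.1, Table 10, sets the Week 12 window at Days 72–127 (target Day 85) and the Week 24 window at Day 128 onward (target Day 169, no upper limit). Only fasting SMPG, the 7-point profile and basal insulin dose are exempt, so HbA1c and FPG are covered. The rule is inclusive: "All non-missing measurements (scheduled or unscheduled) will be used if the measurement date is within the analysis window". If several values share a window, the one nearest the target is used.

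Under Protocol 4.4.3, patients who leave the trial early "undergo all end-of-trial and follow-up assessments/procedures at a visit that should be identified as" the early trial discontinuation visit, and note c in SAP 5.7.1 repeats this. The end-of-trial assessments include HbA1c and FPG. SAP 4.3.1 states "In case of trial discontinuation, HbA1c assessment will be performed at the time of withdrawal"; Protocol 6.1.1 is softer: "HbA1c assessment will be performed at the time of withdrawal, if possible". The only exclusion in SAP 4.3.1 is by window: "If HbA1c measurements fall out of windowed assessments (baseline, Week 12, Week 24), the results for those assessments will be excluded".

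Under SAP 4.3.2, missing values in patients who stopped study drug are imputed, within arm, from patients who also stopped but have an assessed endpoint. Under SAP 4.4.1.1, a missing Week 24 HbA1c counts as not reaching 7.0%.

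**The concern.** Leaving the trial is not one of the listed intercurrent events (Protocol Table 8-1), so the treatment policy strategy does not turn a withdrawal-day value into a Week 24 value. For a patient who leaves on Day 130, the Week 24 result is strictly missing, and the plan sends missing results to multiple imputation. Table 10 makes no use of the visit label that the protocol requires, so this value is treated as observed.

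Three things would follow in the full design:

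- The patient bypasses imputation.
- If study drug stopped at about the same time, a largely on-treatment value joins the donor pool for other discontinuers in that arm.
- A withdrawal value below 7.0% counts as a Week 24 success, where a missing value would count as a failure.

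The exclusion in SAP 4.3.1 does not help, because from Day 72 every date falls in the Week 12 or the Week 24 window.

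**Working it through.** **Windows.** The Table 10 cuts are midpoints between target days: (29 + 57)/2 = 43, (57 + 85)/2 = 71, (85 + 169)/2 = 127. All match the table, so Week 24 starts on Day 128. Visit 17 is schedule Day 168 ± 3 with baseline as Day 0. Table 10 counts first dose as Day 1, so Visit 17 falls on study Days 166–172.

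**Stretch in question.** Days 128–165 are 38 days. They lie 169 − 128 = 41 to 169 − 165 = 4 days before target, and 127/7 = 18.1 to 164/7 = 23.4 weeks after first dose.

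**Patients affected, full design.** The 630 patients and 10% dropout come from SAP 2. Even timing over 168 days is an assumption.

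- Dropouts: 0.10 × 630 = 63.
- Leaving on Days 128–165: 63 × 38/168 = 14.25, or 2.26% of 630 (about 7 per arm).
- If half give a sample (assumed): 7.1, or 1.13%.
- At 5% dropout: 31.5 × 38/168 = 7.1. At 15%: 94.5 × 38/168 = 21.4.

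**Direct effect on the treatment difference.** This is the share affected times the between-arm difference in (withdrawal value − true Week 24 value), assumed to be 0.1 to 0.5 points.

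- All sampled: 0.0226 × 0.1 = 0.002; 0.0226 × 0.5 = 0.011.
- Half sampled: 0.0113 × 0.1 = 0.001; 0.0113 × 0.5 = 0.006.

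**Donor effect.** Patients leaving before Day 128 number 63 × 127/168 = 47.6, or 7.56% of 630. Assume that withdrawal draws are 25% to 50% of donors.

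- Low: 0.0756 × 0.25 × 0.1 = 0.002.
- High: 0.0756 × 0.50 × 0.5 = 0.019.

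This treats imputation as copying a donor mean. The planned regression conditions on baseline and Week 12, so the figure is only a rough guide.

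**Scale.** The two upper figures sum to 0.011 + 0.019 = 0.030, a tenth of the 0.3 margin. At the design SD of 1.1 and 283 per arm, the 95% half-width is 1.96 × 1.1 × √(2/283) = 0.18. At 15% dropout the upper figures grow by half, to 0.017 and 0.028.

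**Who is not affected.** Protocol 4.4.3 says "All patients who discontinue study drug treatment will be followed up per the methods specified in this protocol", so a patient who stops drug but attends Visit 17 has a value nearer Day 169, and that value is used. Patients who cannot be reached ("If the patient continues to be unreachable, they will be considered to have withdrawn from the trial", Protocol 4.4.2) give no draw. The per-protocol set requires trial completion. Estimand 1b drops values taken after drug was stopped.

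**What remains after termination.** SAP 4.1 and 5.2 reduce the analyses and make efficacy descriptive. Appendix 6 lists no imputation and no ANCOVA. The outputs touched are the HbA1c and FPG box plots, the bar chart of HbA1c below 7.0% at Week 24, and Listing 16.2.8.

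**The case for a change.** The case for a change is that the protocol already requires a distinct visit label, so one extra rule could route these draws to a separate analysis visit. The SAP is also uneven: Week 24 fasting SMPG comes from the 7 days before the site visit, while Week 24 HbA1c may date from Day 128. Termination may have made such draws common. On 27 June 2023 the first patient, randomized on 20 December 2022, was on Day 190, and anyone randomized from 14 January to 20 February 2023 was on Days 165 to 128. Final draws taken on that date would carry the Week 24 label.

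The textual part stands: nothing in the SAP separates these values. The rest does not lead to a better rule.

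- **The SAP does not overlook the draws.** Section 4.3.1 mentions the withdrawal sample and, in the next sentence, excludes only values outside the windows. The midpoint cut is ordinary practice.
- **Removal has its own cost.** A measured value at 18 to 23 weeks would be replaced by one predicted from baseline and Week 12. Thinning the donor pool also makes the SAP 4.3.2 fallback more likely, in which missing values are sampled around the patient's baseline.
- **A Day 166 cut would be arbitrary.** It discards a Day 165 value, 4 days from target, and turns a measured result below 7.0% into a modelled failure. Yet a withdrawal draw on Day 127, 42 days after its target, stays as Week 12.
- **The visit label misses similar cases.** End-of-treatment assessments are also made when drug is permanently stopped (Protocol 4.4.1.1) or before rescue (Protocol 5.2.2). If such a patient is later lost, that value still becomes Week 24.

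On termination, the documents do not say whether ongoing patients had a final draw at once or went on to Visit 17, so the number of early values, if any, is unknown. Showing the study day in the listing or adding a footnote would be a courtesy to readers. The listing is known only by its title and may already show dates.

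**Conclusion.** The observation is accurate, but it does not call for a change. Table 10 makes a fair trade-off: it keeps a real, slightly early measurement instead of a modelled one. In the full design about 14 of 630 patients would be involved, or about 7 to 21 for dropout of 5% to 15%. At 10% dropout the treatment difference would shift by at most about 0.011 points directly and 0.019 through donors, against a 0.3 margin. These figures rest on even dropout timing, on every withdrawing patient giving a sample, and on between-arm gaps and donor shares that have no source in the documents. No direction of bias can be shown, and none can be assumed to favour either arm. In the abbreviated report no test or interval depends on the point, so only the labelling of observed-case displays is left, and that changes no conclusion.
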